#### 8.3.3 Treatment groups for analysis

Summaries will be presented according to the following overall treatment groups:

Primary:

- **Randomised Anifrolumab 300 mg:** Subjects randomised to anifrolumab 300 mg in Studies D3461C00004 or D3461C00005 using all data from randomisation to end of LTE, including follow-up data.
- **Randomised Placebo:** Subjects randomised to placebo in Studies D3461C00004 or D3461C00005 using data from randomisation up until switch to anifrolumab 300 mg (ie, up to Week 52 in Phase 3 pivotal studies) or to end of LTE for subjects re-randomised to placebo, respectively, in the LTE.

Supportive:

- **Placebo Feeder + Placebo LTE:** Subjects randomised to placebo in Studies D3461C00004 or D3461C00005 and re-randomised to placebo in LTE using all data from randomisation to end of LTE. Data from subjects discontinuing from the investigational product in Studies D3461C00004 or D3461C00005, or who elect not to participate in the LTE, but who would have been re-randomised to placebo are included in this treatment group up to withdrawal.
- **All Anifrolumab:** Subjects randomised to anifrolumab in studies D3461C00004 or D3461C00005, regardless of dose, and subjects randomised to placebo in studies D3461C00004 or D3461C00005 and then re-randomised to anifrolumab 300 mg in LTE, using all data from randomisation or switch to anifrolumab, respectively, to end of LTE.

Additional supportive:

- **Placebo Feeder + Placebo LTE:** As described above but using data collected during the LTE study only, ie, reduced to subjects enrolled in the LTE study.
- **Placebo Feeder + Anifrolumab 300 mg LTE:** Subjects randomised to placebo in studies D3461C00004 or D3461C00005 and then re-randomised to anifrolumab 300 mg in LTE using data from switch to end of LTE.
- **Anifrolumab 150 mg Feeder + Anifrolumab 300 mg:** Subjects randomised to anifrolumab 150 mg in Study D3461C00005 and then switched to anifrolumab 300 mg in LTE using data from switch to end of LTE.

In addition, supplemental summaries with the data collected in the LTE only (excluding the feeder studies) will be provided.

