## 1.2 Study design

This is a Phase 3, multicentre, multinational, randomised, double-blind, placebo-controlled extension study characterising the long-term safety and tolerability of an IV treatment regimen of anifrolumab (300 mg) versus placebo in subjects with moderately to severely active systemic lupus erythematosus (SLE) who completed a Phase 3 study (D3461C00004 or D3461C00005) through the 52-week double-blind treatment period.

Approximately 575 subjects from Studies D3461C00004 or D3461C00005 (also referred to as the feeder studies) who were previously treated with anifrolumab (150 or 300 mg) or placebo for 52 weeks while receiving standard of care (SOC) treatment and who are willing to continue treatment may participate in the long-term extension (LTE) study if all eligibility criteria are met. Subjects will receive either a fixed IV dose of 300 mg anifrolumab every 4 weeks (Q4W) for up to 39 doses (LTE Week 0 to LTE Week 152) or placebo. Investigational product (IP) will be administered as an IV infusion via an infusion pump over a minimum of 30 minutes, Q4W.

In order to ensure that subjects with active SLE who enter the LTE will have adequate treatment of their disease in this 3-year blinded, placebo-controlled extension study, Investigators will be allowed to change the background SOC treatment for SLE during the course of the study. This LTE protocol allows for adding a new oral immunosuppressant or changing background immunosuppressants, as well as for flexible oral corticosteroids (OCS) use, so that subjects may achieve adequate control of their disease on study. However, it is recommended that subjects receive the lowest possible corticosteroid dose.

In the LTE study, treatment assignment will follow an Interactive Voice/Web Response System (IXRS) algorithm as follows:

- Subjects previously treated with anifrolumab 300 mg IV will stay on blinded treatment
- Subjects previously treated with anifrolumab 150 mg will switch to blinded anifrolumab 300 mg
- Subjects previously randomised to placebo will be re-randomised 1:1 to blinded anifrolumab 300 mg or placebo

Therefore, in the LTE study subjects will receive double-blind treatment with either anifrolumab 300 mg or placebo in an approximate ratio of 4:1.

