### **1.3 Number of subjects**

No formal comparisons are planned in this study; point estimates and confidence intervals (CIs) will be presented for each treatment group separately. The sample size is not based on statistical considerations, but is defined as all subjects who completed the treatment period in

the Phase 3 feeder Studies D3461C00004 or D3461C00005 (through Week 52) and met all study eligibility criteria. Assuming annual dropout rates of 30%, 30%, and 20% following placebo, anifrolumab 150 mg, and anifrolumab 300 mg, and that 90% of the subjects completing studies D3461C00004 or D3461C00005 enter the LTE, follow-up times of approximately 893, 517, and 1343 subject years for the “Randomised Anifrolumab 300 mg,” “Randomised Placebo,” and “All Anifrolumab” treatment groups are expected. Given this exposure, the 95% CIs for an AESI for which the observed incidence rate is 10 events in 1000 subject years will be 5.21 to 19.21 for “Randomised Anifrolumab 300 mg,” and 4.24 to 23.57 for “Randomised Placebo.” For an AESI for which the observed incidence rate is 1 event in 1000 subject years, the 95% CI will be 0.18 to 5.42 for “All Anifrolumab” (0.13 to 7.95 for “Randomised Anifrolumab 300 mg”), and 0.07 to 15.25 for “Randomised Placebo,” using the Rothman-Greenland Method ([Rothman and Greenland, 1998](#)).

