#### 2.1.6 Treatment groups for analysis

Summaries will be presented according to the following combined treatment groups. If not mentioned otherwise, data from subjects discontinuing from the investigational product in studies D3461C00004 or D3461C00005, or who elect not to participate in the LTE, will be considered up to the adjusted analysis-defined visit window of Week 52 (ie, up to Day 378).

Primary:

- **Randomised Anifrolumab 300 mg:** Subjects randomised to anifrolumab 300 mg in studies D3461C00004 or D3461C00005 using all data from start of feeder study to end of LTE.
- **Randomised Placebo:** Subjects randomised to placebo in studies D3461C00004 or D3461C00005 using data from start of feeder study up until switch to anifrolumab 300 mg or to end of LTE for subjects re-randomised to placebo in LTE, respectively.

Supportive:

- **Placebo Feeder + Placebo LTE:** Subjects randomised to placebo in Studies D3461C00004 or D3461C00005 and re-randomised to placebo in LTE using all data from start of feeder study to end of LTE. Data from subjects not randomised into the LTE for any reason but that would have been re-randomised to placebo are included in this treatment group up to Week 52. Subjects who are not randomised into the LTE study will be assigned to Placebo or anifrolumab 300 mg via a

separate randomization process in order to determine who would have been re-randomised to placebo.

- **All Anifrolumab:** Subjects randomised to anifrolumab in studies D3461C00004 or D3461C00005, regardless of dose, and subjects randomised to placebo in studies D3461C00004 or D3461C00005 and then re-randomised to anifrolumab 300 mg in LTE, using all data from start of feeder study or switch to anifrolumab, respectively, to end of LTE. Baseline data from the feeder study will be included for all subjects.

Additional supportive:

- **Placebo Feeder + Anifrolumab 300 mg LTE:** Subjects randomised to placebo in studies D3461C00004 or D3461C00005 and then re-randomised to anifrolumab 300 mg in LTE using data from start of feeder study to end of LTE. Data from subjects not randomised into the LTE for any reason, but that would have been re-randomised to anifrolumab 300 mg are included in this treatment group up to Week 52. Subjects who are not randomised into the LTE study will be assigned to Placebo or anifrolumab 300 mg via a separate randomization process in order to determine who would have been re-randomised to anifrolumab 300 mg.

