Cardiovascular outcome events as determined by the CV-EAC will be presented separately, summarising the number of AEs submitted for adjudication and the outcomes of the adjudication including MACE classification. Site reported cardiovascular AEs, cardiovascular SAEs, and their corresponding adjudicated outcomes will be listed.

The time to first onset of an AE in an AESI category will be presented separately for each AESI category as a Kaplan-Meier plot annotated with the number of subjects at risk every 6 months.

Furthermore, the alternative event rates per 100 subject years for the first onset of herpes zoster will be summarized for events overall and by time intervals). The following subcategories will also be considered in this summary: SAE (including events with outcome of death), AE leading to discontinuation, and AE by maximum intensity (mild, moderate, and severe). This summary will also be presented for the additional supportive treatment groups placebo feeder + anifrolumab 300 mg LTE, and anifrolumab 150 mg feeder + anifrolumab 300 mg LTE.

Furthermore, AESIs (by event type and preferred term), SAEs (during treatment and during follow-up separately, by system organ class and preferred term) during LTE will be summarised by LTE treatment group. Summaries of deaths, AESIs by time interval and SAEs by time interval will also be presented for the additional supportive treatment groups placebo feeder + anifrolumab 300 mg LTE, and anifrolumab 150 mg feeder + anifrolumab 300 mg LTE.

The event rate per 100 subject years and number and percentage of subjects with at least one anaphylaxis, hypersensitivity, and infusion-related reaction (investigator), respectively, will be summarised overall as well as for the following respective subcategories: SAE (including events with outcome of death), AE leading to discontinuation, and AE by maximum intensity (mild, moderate, and severe). Furthermore, these AE categories will be presented graphically over time as percentage of subjects with a respective AE at a respective visit according to the definition as given in Section 3.1.1. These summaries will also be presented for the additional supportive treatment groups placebo feeder + anifrolumab 300 mg LTE, and anifrolumab 150 mg feeder + anifrolumab 300 mg LTE.

Infections, opportunistic infections, and non-opportunistic infections will be summarised with the same subcategories as given above. This summary will also be presented for the additional

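### The SAP's combined-data group Placebo Feeder + Anifrolumab 300 mg LTE counts the placebo year (about 38% of its person-time), so its infection, reaction and overall zoster rates are blended, where the protocol counts from the switch

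*SAP*

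**What the plan says.** Protocol 8.3.3 lists Placebo Feeder + Anifrolumab 300 mg LTE among the additional supportive groups: feeder-placebo subjects "re-randomised to anifrolumab 300 mg in LTE using data from switch to end of LTE".

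SAP 2.1.6 uses the same name for two data spans:

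- **Combined feeder and LTE tables:** subjects "re-randomised to anifrolumab 300 mg in LTE using data from start of feeder study to end of LTE". Feeder-placebo subjects who did not enter the LTE are given a notional assignment, and those who "would have been re-randomised to anifrolumab 300 mg are included in this treatment group up to Week 52".
- **LTE-only tables:** data from the switch onward, as in the protocol.

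SAP 4.2.1.1 adds the combined version as an extra column to the overall AE summary, to deaths, to AESIs and SAEs by time interval, to herpes zoster, and to anaphylaxis, hypersensitivity and infusion-related reactions. It also adds it for infections: "Infections, opportunistic infections, and non-opportunistic infections will be summarised with the same subcategories as given above".

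The legible part of SAP section 6 describes the treatment-group changes as clarification of which data each group includes. It does not mention the change of start point. Part of that section is blacked out, so a specific statement there cannot be excluded.

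**The concern.** A column whose label ends in anifrolumab 300 mg LTE would carry a rate made partly from placebo events and placebo time. The rules in SAP 3.1.1 that remove time on the other treatment are written only for Randomised Placebo and All Anifrolumab, so nothing removes the placebo year here.

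These subjects have their first anifrolumab exposure in the LTE, which makes them informative about first-exposure reactions and early infections. Placebo time in the same rate dilutes that information towards the placebo level. A reader who moves between a combined table and an LTE-only table would also meet one label with two meanings.

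**Working it through.** **Inputs (SAP 1.2 and 1.3)**

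- "Assuming annual dropout rates of 30%, 30%, and 20% following placebo, anifrolumab 150 mg, and anifrolumab 300 mg".
- "90% of the subjects completing studies D3461C00004 or D3461C00005 enter the LTE".
- "Subjects previously randomised to placebo will be re-randomised 1:1 to blinded anifrolumab 300 mg or placebo".
- Stated totals for Randomised Anifrolumab 300 mg, Randomised Placebo and All Anifrolumab: "follow-up times of approximately 893, 517, and 1343 subject years".
- Feeder 52 weeks, taken as 1 year. LTE treatment 156 weeks, taken as 3 years.

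**Assumptions.** Dropouts leave mid-year on average. Dropout is 20% per year after any switch to 300 mg. The 12-week follow-up is not modelled separately.

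**Step 1. Person-years per subject**

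- Feeder year: 1 − d/2, so 0.90 at 20% dropout and 0.85 at 30%.
- Three LTE years at 20%: (1 + 0.8 + 0.64) × 0.90 = 2.196.
- Three LTE years at 30%: (1 + 0.7 + 0.49) × 0.85 = 1.8615.
- LTE entry per feeder-placebo or 150 mg subject: 0.70 × 0.90 = 0.63. Per 300 mg subject: 0.80 × 0.90 = 0.72.

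**Step 2. Reproduce the stated totals.** The documents do not give feeder arm sizes. Back-solving from the three totals gives 359.9, 359.9 and 90.0, so 360 (300 mg), 360 (placebo) and 90 (150 mg):

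- Randomised 300 mg: 360 × (0.90 + 0.72 × 2.196) = 893.2.
- Randomised Placebo: 360 × (0.85 + 0.5 × 0.63 × 1.8615) = 517.1.
- All Anifrolumab: 893.2 + 90 × (0.85 + 0.63 × 2.196) + 180 × 0.63 × 2.196 = 893.2 + 201.0 + 249.0 = 1343.2.

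Three sizes fitted to three totals is a weak test, although sizes this close to whole tens support the model. Keeping 30% dropout after the switch gives 1286 at these sizes; it would need about 118 subjects on 150 mg to return 1343. The model implies about 543 LTE entrants, against the planned figure of about 575.

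**Step 3. Placebo share of the combined column.** Arm size cancels:

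0.85 / (0.85 + 0.63 × 2.196) = 0.85 / 2.233 = 38.1%

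For 180 subjects this is 153.0 placebo and 249.0 anifrolumab subject-years. On the protocol's span the placebo share is 0%.

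| Scenario | Placebo share |
|---|---|
| No dropout, all enter: 1/4 | 25% |
| LTE entrants only: 1/(1 + 2.196) | 31.3% |
| Exponential instead of mid-year dropout | 37.9% |
| Base case | 38.1% |
| 30% dropout kept after switch: 0.85/(0.85 + 0.63 × 1.8615) | 42.0% |

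**Step 4. Effect on a rate (illustration, assumed rate ratios).** With the placebo rate set to 1:

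- Doubling: 0.381 × 1 + 0.619 × 2 = 1.62, which is 19% below 2.
- Tripling: 0.381 × 1 + 0.619 × 3 = 2.24, which is 25% below 3.
- A doubling at the ends of the range: 0.25 + 0.75 × 2 = 1.75, and 0.42 + 0.58 × 2 = 1.58.

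The mix is approximate. SAP 3.1.1 counts subjects with an event, not events. A subject with an infection in the placebo year is already counted, and a later one on anifrolumab adds nothing.

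**Step 5. Effect on a percentage.** The reaction summary also gives percentages, and SAP 4.1.3 makes all subjects in the group the default denominator. Under the plan's assumptions, 1 − 0.63 = 37% of them never receive anifrolumab.

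**Step 6. What can be separated elsewhere in SAP 4.2.1.1**

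| Output for this group | Other route to time on anifrolumab |
|---|---|
| Overall AE summary | Repeated for the LTE only |
| AESIs, SAEs | By interval, with Year 1 the feeder period (SAP 3.1.1); also by LTE group |
| Herpes zoster | By interval; only the overall figure is blended |
| Anaphylaxis, hypersensitivity, infusion reactions | Plot by visit; anaphylaxis as an AESI; preferred-term rates during LTE treatment. No from-switch version of the summary with its subcategories |
| Infections | Serious non-opportunistic and opportunistic infections as AESIs. No from-switch version of the all-infection figure or the subcategories |

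**The case against.** A reader might infer that the SAP has dropped the protocol's from-switch definition. It has not: that definition stays in SAP 2.1.6 for the LTE-only tables.

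A reader might also infer that the zoster signal, an identified risk, is hidden in this group, or that first-exposure reactions cannot be seen. The documents do not support either. Zoster is tabulated by time interval with the feeder period as its own interval, and reactions are plotted by visit, with visits defined by infusion date.

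Nor does the blending reach the main safety results. The main assessment sets Randomised Anifrolumab 300 mg beside Randomised Placebo, rare events use All Anifrolumab, which counts switchers only from the switch, and no formal comparison is planned.

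There is also a design argument. The column mirrors Placebo Feeder + Placebo LTE, which runs from feeder start and includes notionally assigned non-entrants, and Protocol 3.4 provides for that assignment. A summary of the whole treatment sequence, as randomised, is coherent.

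All of this stands, and it limits the point to a few supportive outputs. It does not explain why the span differs from Protocol 8.3.3, nor does it supply a from-switch rate in the infection and reaction summaries.

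**Conclusion.** The mismatch between Protocol 8.3.3 and SAP 2.1.6 is real, and describing it as clarification understates it. In the combined tables about 38% of this group's person-time is placebo, with a range of 25% to 42% across the scenarios shown. The figure rests on the SAP's planning dropout and entry rates, mid-year dropout, and inclusion of non-entrants; it does not depend on the inferred arm sizes. The dilution of 2 to about 1.6 is an illustration with an assumed effect.

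The consequence is confined to the infection summary, the anaphylaxis, hypersensitivity and infusion-reaction summary with its subcategories, and the overall zoster rate. No primary or All Anifrolumab result changes. It is worth correcting because the direction is predictable, the protocol already has the cleaner span, and the data set for it exists.

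**What to change.** 1. In the infection summary, the anaphylaxis, hypersensitivity and infusion-reaction summary, and the overall zoster rate, report this group's rates and percentages from the first LTE dose in LTE entrants, using the existing LTE-only group. Alternatively, split the column into before and after the switch.
2. Handle Anifrolumab 150 mg Feeder + Anifrolumab 300 mg LTE the same way. It has the same mismatch (from the switch in Protocol 8.3.3, from feeder start in SAP 2.1.6), although all its time is on anifrolumab.
3. Give the two data spans different labels, for example whole sequence and from switch.
4. State in SAP section 6 that the start point of these groups differs from the protocol, and why.

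The cost is SAP wording and a few extra table runs on a supportive column. No new data or derivations are needed.

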**Figure 1 Primary: Combined treatment groups Randomised Anifrolumab 300 mg and Randomised Placebo (main comparison)**

**Figure 2 Supportive: Combined treatment groups Placebo Feeder + Placebo LTE and All Anifrolumab**

**Figure 3 Additional Supportive: Combined treatment groups Placebo Feeder + Anifrolumab 300 mg LTE and Anifrolumab 150 mg Feeder + Anifrolumab 300 mg LTE**

[figure not shown]

Additional summaries for data collected during the LTE study only will be presented according to the following supportive LTE treatment groups:

- **Randomised Anifrolumab 300 mg:** As described above but using data collected during the LTE study only, ie, reduced to subjects enrolled to the LTE study.

- **Placebo Feeder + Placebo LTE:** As described above but using data collected during the LTE study only, ie, reduced to subjects enrolled to the LTE study.
- **Placebo Feeder + Anifrolumab 300 mg LTE:** Subjects randomised to placebo in studies D3461C00004 or D3461C00005 and then re-randomised to anifrolumab 300 mg in LTE using data from switch to end of LTE.
- **Anifrolumab 150 mg Feeder + Anifrolumab 300 mg LTE:** Subjects randomised to anifrolumab 150 mg in Study D3461C00005 and then switched to anifrolumab 300 mg in LTE using data from switch to end of LTE.

**Figure 4 LTE treatment groups**

## 2.2 Protocol deviations

All protocol deviations identified during monitoring of the study will be recorded in the clinical trial management system (CTMS). Important protocol deviations (IPDs) during the LTE study are a subset of protocol deviations that may greatly impact the completeness, accuracy, and/or reliability of the study data or that may significantly affect a subject’s rights, safety, or well-being.

Protocol deviations will be classified as important or not important by the PRA Medical Monitor as defined in the Protocol Deviation Guidance based on periodic reviews of CTMS deviation reports and blinded delivery reviews (BDR). The Sponsor then reviews the classification and provides the final determination. The list of important protocol deviations will be finalised and documented prior to unblinding the study data.

COVID-19 related protocol deviations should be recorded prefixed by “COVID-19”.

Only important protocol deviations (any, COVID-19 related, and not COVID-19 related) will be listed and tabulated in the Clinical Study Report (CSR).

### 3. PRIMARY AND SECONDARY VARIABLES

If not stated otherwise, not only data collected during the LTE study but also data collected in the Phase 3 feeder Studies D3461C00004 and D3461C00005 will be considered. If not stated otherwise, all references to Day 1 and date of first dose of investigational product, respectively, refer to the respective day in the Phase 3 feeder studies. The date of last dose of investigational product refers to the last dose during the LTE study for subjects who started the LTE study and to the last dose in the Phase 3 feeder studies for subjects not continuing in the LTE study.

Baseline is defined as baseline of the Phase 3 feeder studies, i.e., the last non-missing measurement prior to dose administration on Day 1. If the Day 1 value is missing or is invalid or is collected after administration of investigational product, the latest assessment prior to dose administration on Day 1 will serve as baseline.

[REDACTED]

[REDACTED]

If not stated otherwise, change from baseline will be calculated as value at the respective post-baseline time point minus value at baseline.

#### 3.1 Safety variables

The following primary safety data will be collected: AESIs and SAEs.

Other safety variables include adverse events (AEs), vital signs, physical examination, electrocardiograms (ECGs), flares as defined by a modification of the SELENA Flare Index using the SLEDAI-2K, haematology, clinical chemistry, and urinalysis.

Change from baseline to each post-treatment time point where scheduled assessments were made will be calculated for relevant measurements.

If not stated otherwise, on-treatment values are defined as values with an assessment date after the first administration of investigational product and on or before the date of last administration of investigational product + 28 days.

The restriction that “data from subjects discontinuing from the investigational product in studies D3461C00004 or D3461C00005, or who elect not to participate in the LTE, will be considered up to the adjusted analysis-defined visit window of Week 52 (ie, up to Day 378)” (see section 2.1.6) does only apply to visit-based analyses of safety variables.

